9.1. Injection Site Evaluation

The number and percentage of subjects with an injection site reaction will be summarized, along with the type of reaction. All injection site evaluation information will be provided in a listing.

9.2. Muscle Injection Record

The number and percentage of subjects injecting into each muscle will be summarized. All muscle injection record data will be listed.

9.3. Adverse Events

AEs will be coded using MedDRA version 22 or later. An AE will be considered treatment emergent if the event begins on or after the study medication dose date or if the event begins before and worsens in severity after the study medication dose date. An adverse event with a relationship to study medication of definite, probable, or possible is also considered to be treatment-emergent.

AEs will be summarized by system organ class (SOC) and preferred term (PT). An AE is considered related to study treatment if the relationship is considered as definite, probable, or possible. If the relationship to study treatment is missing, the AE will be counted as definite in summary tables. If the severity is missing, then the AE will be counted as severe in summary tables. Actual missing values will be presented in the listings.

Summary tables will be provided for treatment-emergent AEs (TEAEs) for the following:

- Overall summary of TEAEs
- TEAEs by SOC and PT
- TEAEs by SOC and PT occurring in at least 5% of subjects
- TEAEs by SOC, PT, and maximum severity
- TEAEs by SOC, PT, and strongest study medication relationship
- Treatment-related TEAEs by SOC and PT
- Serious TEAEs by SOC and PT
- TEAEs resulting in study medication discontinuation by SOC and PT

[REDACTED]

The overall summary of TEAEs will include the number and percentage of subjects with a TEAE, with treatment-related TEAEs, with serious TEAEs, [REDACTED], and with TEAEs leading to death. For TEAE summaries, the number and percentage of subjects will be presented by SOC and PT by treatment. Subjects will be counted only once for each SOC and for each PT within each SOC. For summaries by maximum severity and strongest relationship, if a subject has the same event more than once, the subject will be included only once at the worst severity or strongest relationship. Summary tables by SOC and PT will be sorted in descending frequency by SOC and then by PT within each SOC by the DAXI 500 U column. All AEs will be included in the listings. Listings will be provided for all AEs, serious AEs, and AEs resulting in study medication discontinuation.

This document is confidential.

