6.2 Adverse Events

6.2.1 Assessment of Adverse Events:

Adverse Events (AEs) will be graded as mild, moderate, or severe as defined in Section 6.2.2.3 of this protocol.

AEs will be evaluated at the Injection visit post-treatment, follow-up Weeks 2, 4, 6, 8, 12, 16, 20, 24, 28, 32 and 36/EOS, if applicable.

Adverse events will be reported by the Sponsor in accordance with "21CRF part 312.32 and Guidance for Industry and Investigators: Safety Reporting Requirements." The Investigator will report any serious adverse events (SAEs) to the IRB.

Subjects should be told to seek immediate medical attention if they experience any abnormal symptoms after investigational product administration, especially:

- Generalized loss of strength and muscle weakness
- Difficulty swallowing, breathing or speaking
- Extreme tiredness
- Loss of bladder control
- Symptoms of allergic reaction (rash, itching, etc.)

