6.2.2 Adverse Events and Serious Adverse Events

6.2.2.1 Definition of Adverse Events

For this protocol, an adverse event (AE) is any untoward medical occurrence (e.g., sign, symptom, disease, syndrome, intercurrent illness, clinically significant abnormal laboratory finding, injury or accident) that emerges or worsens following administration of investigational product and until the end of trial participation that may not necessarily have a causal relationship to the administration of the investigational product. An AE can therefore be any unfavorable and/or unintended sign (including a clinically significant abnormal laboratory result), symptom, or disease temporally associated with the use of an investigational product, whether or not considered related to the investigational product. A treatment-emergent AE (TEAE) is one that occurs after any period of exposure to treatment.

Pre-existing conditions, which increase in frequency or severity or a change in nature as a consequence of an investigational product use will also be considered an adverse event.

An unexpected AE is an adverse reaction, the nature or severity of which is not consistent with the applicable product information (e.g., Investigator's Brochure for an unapproved investigational product or package insert/summary of product characteristics for an approved product). Any clinically significant change in the study safety evaluations, (e.g., vital signs, laboratory results, ECG, injection site evaluation, physical/neurological examinations, etc.) post-treatment must be reported as an AE.

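### For adverse events with pre-dose onset that are rated unrelated, the SAP's treatment-emergent rule omits worsening on the injection day and worsening without a change of severity grade

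*SAP*

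**What the plan says.** SAP 9.3 gives three routes to treatment-emergent status.

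1. Onset: "An AE will be considered treatment emergent if the event begins on or after the study medication dose date".
2. Earlier onset with worsening: "if the event begins before and worsens in severity after the study medication dose date".
3. Relatedness: "An adverse event with a relationship to study medication of definite, probable, or possible is also considered to be treatment-emergent".

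The same section adds: "If the relationship to study treatment is missing, the AE will be counted as definite in summary tables". It does not say whether that imputed value also sets the TEAE flag. Events that are not TEAEs are still reported individually: "All AEs will be included in the listings".

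On the protocol side, 6.2.2.1 defines an AE as an untoward occurrence "that emerges or worsens following administration of investigational product", and a TEAE as one occurring after any exposure. The same section names further kinds of change: "Pre-existing conditions, which increase in frequency or severity or a change in nature", but limits that sentence to changes caused by the product. Section 6.2.1 schedules a check on the dosing day: "AEs will be evaluated at the Injection visit post-treatment". Section 6.2.2.4 treats a condition present at screening as baseline, requires its later deterioration to be recorded as an AE, and asks for severity changes and for the onset and duration of each episode of an intermittent event.

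**The concern.** Route 1 includes the dose date. Route 2, in the same sentence, does not. Read literally, an event that began before dosing and is found worse at the post-injection check on Day 1 fails route 2. Route 2 also recognizes only a higher severity grade, so an event that becomes more frequent or changes in nature at the same grade fails it too.

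Route 3 rescues such an event only when the investigator rates it at least possibly related. A TEAE table is meant to count events whatever their cause. For these types of worsening, entry would depend on the causality rating. The table by strongest relationship would then include the related cases and drop the unrelated ones, so its unrelated category would be incomplete for these events.

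**Working it through.** The plan states no figure to reproduce, so the check applies the three routes to every kind of event with recorded pre-dose onset.

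Inputs: type of change (severity, frequency, nature; protocol 6.2.2.1), timing (dose day after injection, or a later day; protocol 6.2.1 and SAP 9.3), and causality (related meaning possible or stronger, or unrelated; SAP 9.3). Number of cases: 3 × 2 × 2 = 12.

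| Change | When | Rated related | Rated unrelated |
|---|---|---|---|
| Severity | dose day | TEAE (route 3) | not a TEAE |
| Severity | later day | TEAE (routes 2 and 3) | TEAE (route 2) |
| Frequency | dose day | TEAE (route 3) | not a TEAE |
| Frequency | later day | TEAE (route 3) | not a TEAE |
| Nature | dose day | TEAE (route 3) | not a TEAE |
| Nature | later day | TEAE (route 3) | not a TEAE |

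Related: 6 of 6 captured. Unrelated: 1 of 6 captured. Total: 6 + 1 = 7 of 12, with 5 missed, all of them unrelated. If route 2 covered the dose day after injection and all three types of change, 12 of 12 would be captured. These are counts of logical cases, not event rates. The documents give no AE rates, so the number of events affected cannot be estimated.

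Weight of one subject: assuming about 128 subjects allocated equally to four arms, 128 / 4 = 32 per arm and 1/32 = 3.1 percentage points. SAP 9.3 counts a subject once per system organ class and once per preferred term within it, so a row moves only if that subject has no other TEAE in it.

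SAP 9.3 also plans a table of TEAEs in at least 5% of subjects, without saying whether the threshold applies per arm or overall. Per arm, 1/32 = 3.1% is below it and 2/32 = 6.3% is above. Overall, 6/128 = 4.7% is below and 7/128 = 5.5% is above. Either way, one subject matters for display only when a term sits at the threshold.

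**The case against.** A reader might infer that the SAP excludes all Day 1 worsening and all same-grade worsening of pre-existing events. It does not: the relatedness sentence brings in every event rated possible or stronger, whatever the day or type of change. The protocol sentence that names frequency and nature is itself limited to product-caused changes, which would normally be rated related and so are already counted.

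The recording rules narrow the gap further. A deterioration of a condition present at screening is to be recorded as an AE. If that record is dated at the deterioration, route 1 captures it. Intermittent events need an onset for each episode. What remains is then mainly unrelated events that start between screening and injection, at most 21 days. The SAP also uses the word after loosely. In 6.2, the study-day formula for dates after dosing must include the dose date for that day to be Day 1, and 7.5.2 mixes both forms in one definition.

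Much of this stands, and it makes the point small. It does not remove it. The general AE definition in 6.2.2.1 covers worsening without a causal limit or a severity limit. Section 6.2.2.4 does not say which onset date a deterioration record carries, and documenting each episode is not the same as opening a separate AE record. Route 2 itself presumes that records with pre-dose onset exist. Loose usage elsewhere is a reason to make the wording exact where a flag is programmed from it.

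Three other inferences go too far. That every AE table is restricted to TEAEs cannot be verified, since redacted blocks follow the table list in 9.3 and sit between 9.3 and 9.5 in the contents. That every missed event shifts a rate by 3 points ignores the once-per-subject counting. That becoming serious is a kind of worsening the protocol names is not so: 6.2.2.1 names frequency, severity and nature.

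**Conclusion.** The point holds in a limited form and is minor. For events recorded with pre-dose onset and rated unrelated, SAP 9.3 as written is narrower than protocol 6.2.2.1: worsening on the injection day after dosing, or without a grade change, reaches the listings but none of the visible TEAE tables. The size in events is unknown and probably small.

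This rests on two assumptions: that the word after in route 2 is programmed literally, and that some deteriorations are kept under their original pre-dose onset date rather than entered as new events. If either fails, the gap shrinks; if both fail, little is left. Nothing disappears from the report, and no efficacy result is touched.

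**What to change.** Reword the second leg of the SAP 9.3 definition to: *or begins before the injection and worsens (in severity, frequency or nature, as in protocol 6.2.2.1) on or after the dose date, following the injection, regardless of causality rating.*

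State how the worsening is dated. The original onset time cannot serve, because for these events it precedes the injection. Use the severity-change and episode records that protocol 6.2.2.4 requires, and treat a deterioration as starting on the date it worsened. The dating rule matters most for a change in nature, for which 6.2.2.4 lists no separate item. Also state whether a missing relationship, counted as definite in the tables, sets the TEAE flag.

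Cost: one reworded sentence, a short dating rule and a change to the flag derivation, with no new assessments. The downside is that a few more unrelated events may count as TEAEs.

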4.6 Subject Discontinuation/Withdrawal Criteria

Study subjects will receive a one (1) time only treatment for this study. Discontinuation of study treatment is not applicable. However, subjects may choose to discontinue their participation in the follow-up phase at any time.

- If the subject withdraws consent and discontinues from the trial, the Investigator will attempt to determine the reason for discontinuation and record the reason in the subject's trial records and on the case report form (CRF).
- If a subject withdraws consent because of an AE, that AE should be indicated as the reason for withdrawal. In the event of early discontinuation, (i.e., prior to the Final Evaluation) and whenever possible, the subject should be asked to return to the trial center to complete the assessments specified in the Week 12/Early Termination visit. Subjects who withdraw from the trial will not be replaced.
- If at any time during the trial, the Investigator determines that it is not in the best interest of the subject to continue, the subject will be discontinued from participation.
- The Investigator can discontinue a subject from study participation at any time if medically necessary or if the subject has failed to follow trial procedures or to keep follow-up

appointments. Appropriate documentation in the subject's trial record and CRF regarding the reason for discontinuation must be completed. Prior to discontinuing a subject from study participation, the Investigator will discuss his/her intentions with the Medical Monitor or designee.

All subjects who fail to return to the trial center for the required follow-up visits will be contacted by phone to determine the reason(s) why the subject failed to return for the necessary visit or elected to discontinue from the trial. If a subject is unreachable by telephone after a minimum of two (2) documented attempts (one [1] attempt on two [2] different days), a registered letter will be sent requesting that contact be made with the Investigator.

Revance can terminate or to stop the trial at any time. Should this be necessary, both Revance and the Investigator will ensure that proper study discontinuation procedures are completed.

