5.4 End of Study Visit

A participant is considered to have completed the study when the MAS score has returned to baseline levels and the PGIC ≤ 0 , or the Week 36 visit whichever comes first and has completed the last scheduled procedure shown in Table 1.1. Schedule of Study Assessments and Procedures.

Subjects enrolled post COVID-19, after 20 March 2020 will have the EOS Visit at Week 12 as shown in Table 1.2. Table 1.1. Schedule of Study Assessments **and Procedures**.

The EOS Visit may also occur when a subject prematurely withdraws from the study for specific reasons (e.g., AEs, pregnancy, or withdraws consent).

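### SAP 9.3 selects a TEAE table and a listing by study medication discontinuation, which protocol 4.6 calls not applicable in this single-treatment trial; both should be redefined by withdrawal from the study

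*SAP*

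**What the plan says.** Protocol 4.6 (Subject Discontinuation/Withdrawal Criteria) is explicit on treatment: "Study subjects will receive a one (1) time only treatment for this study". It continues: "Discontinuation of study treatment is not applicable". What remains possible is leaving follow-up: "subjects may choose to discontinue their participation in the follow-up phase at any time". For that case the protocol asks for the cause: "If a subject withdraws consent because of an AE, that AE should be indicated as the reason for withdrawal". The same section lets the investigator discontinue a subject for medical necessity, with the reason documented in the CRF. Protocol 5.4 (End of Study Visit) names AEs among the reasons for an early end-of-study visit.

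SAP 9.3 (Adverse Events) includes in its set of TEAE tables "TEAEs resulting in study medication discontinuation by SOC and PT". It adds: "Listings will be provided for all AEs, serious AEs, and AEs resulting in study medication discontinuation". Its overall TEAE summary counts subjects with any TEAE, with treatment-related TEAEs, and then "with serious TEAEs, [REDACTED], and with TEAEs leading to death". A further redaction follows the list of tables.

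SAP 7.1 (Subject Disposition and Withdrawals) tabulates completed and discontinued subjects with the reasons for discontinuation, and adds a disposition listing.

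**The concern.** The SAP's table and listing rest on an event that the protocol says does not apply. A table of this kind normally shows which events made subjects stop, and in which arm. After a single treatment there is no later dose to stop, so the criterion misses the form that an AE-driven stop can take here, which is leaving the study.

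Safety is part of the primary objective, across three doses and placebo. A discontinuation table with no entries in any arm tells the reader nothing about tolerability by dose, and it could sit beside a disposition table that does show AE withdrawals. A reader of the study report would then have two outputs that appear to disagree.

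**Working it through.** The plan states no figure on this point, so there is nothing to reproduce. The check is a comparison of sections, followed by one line of arithmetic for scale.

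**Step 1: what the SAP criterion can select.** Under protocol 4.6 each subject is treated once and treatment discontinuation does not apply. If the field is completed as the protocol says, no event meets the SAP 9.3 criterion and the expected count is 0 in each arm. Two routes to a non-zero count remain:

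- An injection session is cut short by an AE.
- Sites or programmers use the field to mean withdrawal from the study.

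The visible text defines neither case. The output is therefore either empty or of undefined meaning.

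**Step 2: what can happen, and whether it is recorded.** Subjects can leave follow-up. Protocol 4.6 requires the AE to be given as the reason when consent is withdrawn because of it. For discontinuation by the investigator it requires only that the reason be documented. Whether the CRF links either reason to a coded AE record is not visible.

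**Step 3: where an AE-driven withdrawal appears in the visible SAP.**

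- Disposition summary and listing (7.1): as a reason for discontinuation. SAP 6.1 presents summaries by treatment group unless otherwise specified, so the counts should be by arm. No breakdown by system organ class and preferred term is specified there.
- TEAE tables by system organ class and preferred term, severity and relationship, and where applicable the serious TEAE table (9.3): the event is included but not marked as the cause of withdrawal.
- Listing of all AEs (9.3): the event is included.
- Discontinuation table and listing (9.3): the event is not selected, because the criterion is study medication.

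The gap is narrow: no visible output by system organ class and preferred term identifies the TEAEs that led to withdrawal.

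**Step 4: scale.** The planned total is about 128 subjects in four arms. The allocation ratio is not visible, so equal allocation is assumed: 128/4 = 32 per arm.

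- One AE-driven withdrawal: 1/32 = 3.1% of an arm.
- Two: 2/32 = 6.3% of an arm.

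In general the share is k/n for k withdrawals in an arm of n, so it is larger in a smaller arm. The documents give no expected rate of AE withdrawal. These figures show what one or two cases would weigh and do not predict them.

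**The case against.** The strongest reply is that little is lost. The reasons for discontinuation are summarized and listed under SAP 7.1. Every TEAE is in the general tables and every AE is in the listings. A reader might infer from the mismatch that events leading to withdrawal go unreported. The documents do not support that: the subjects are counted by reason and the events are tabulated. Only the link between the two, by system organ class and preferred term, is not visible.

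The second reply concerns redaction. SAP 9.3 has blacked-out text after its list of tables, and a blacked-out category in the overall summary between serious TEAEs and TEAEs leading to death. The contents entry between 9.3 and 9.5 is also blacked out. Any of these could hold a withdrawal summary, so its absence from the full SAP cannot be claimed. This stands, and it limits the second half of the point. It leaves the first half untouched, because the table and listing at issue are in clear text and so is the protocol statement they conflict with.

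The third reply is that zero is not guaranteed. Treatment is an injection session with a record by muscle (SAP 9.2), so an interrupted session is conceivable. This also stands: a reader might infer that the table is zero whatever happens, but the supportable statement is that it is expected to be empty when read literally.

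It is also speculative to say that an empty table would be taken as good tolerability, since the protocol states openly that treatment discontinuation does not apply.

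**Conclusion.** The point holds as a low-severity reporting correction. SAP 9.3 builds one table and one listing on a criterion that protocol 4.6 calls not applicable, so both are expected to be empty in all four arms. This assumes that the field is completed as the protocol describes and that no interrupted injection session is counted. In the unredacted SAP, AE-driven withdrawals appear as such only as reasons in the disposition outputs.

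The documents do not show that such withdrawals are omitted from reporting, nor that a summary identifying the responsible events is absent from the redacted text. The 3.1% and 6.3% figures rest on assumed equal allocation and are illustrative. No endpoint, hypothesis test or analysis population is affected, and the efficacy analyses stand as planned.

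**What to change.** In SAP 9.3, redefine the table as TEAEs leading to withdrawal from the study, by system organ class and preferred term and by arm, and redefine the listing to match. Select events by the AE recorded as the reason for withdrawal of consent or for discontinuation by the investigator, and state which CRF field supplies it. Check that the counts agree with the AE reasons in the SAP 7.1 disposition summary.

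If a redacted output already does this, delete the inapplicable table and listing. If the existing pair is meant to capture interrupted injection sessions, define the term in the SAP and reconcile it with protocol 4.6.

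The cost is a few lines of SAP wording, one table shell and one listing. No new data collection is apparent from the documents, provided that the CRF ties the reason for leaving to an AE record. The sponsor should confirm this before database lock.

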3.4 Endpoints

- Co-Primary Endpoints
 - Mean change from baseline in muscle tone measured with the MAS in the suprahypertonic muscle group (SMG) of the elbow, wrist, OR finger flexors at Week 6
 - Mean score of the PGIC at Week 6

3.5 **Duration of Trial**

To provide a sufficient amount of time to document the duration of effect and safety profile of DAXI administered doses, all subjects will be prospectively followed for a minimum of 12 weeks and a maximum of 36 weeks. With a median duration of effect of at least 24 weeks experienced by adult subjects with cervical dystonia given a single treatment of DAXI for injection in the RT002-CL005 Study and adults with glabellar lines treated with a single treatment of DAXI for injection from the SAKURA Studies, it is scientifically justifiable to follow adult subjects with upper limb spasticity treated with DAXI for injection for up to 36 weeks.

Due to the COVID-19 pandemic impact study enrollment, visits, and conduct, subjects enrolled after the 20 March 2020 screening and enrollment hold will complete the study at Week 12. Subject participation may be terminated early for continuing or emergent safety concerns related to COVID-19. Sufficient results should be available to make informed decisions for program development.

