3.4. Brief Description

This is a Phase 2, randomized, double-blind, placebo-controlled, parallel group, dose ranging, multi-center trial to evaluate the efficacy and safety of DAXI for injection in the treatment of ULS in adults after stroke or TBI. The trial will be conducted at approximately 30 sites across the United States.

Approximately 128 subjects with ULS will be randomly assigned

This document is confidential.

The co-primary efficacy endpoints are the mean change from baseline in muscle tone measured using the Modified Ashworth Scale (MAS) in the suprahypertonic muscle group (SMG) of the elbow, wrist, or finger flexors at Week 6 and the mean score on the Physician Global Impression of Change (PGIC) at Week 6.

- For subjects enrolled before COVID-19:
 - The end of study visit for a given subject can occur at Week 12 if the change in MAS score in the SMG is < 1-point reduction from baseline AND the PGIC score is ≤ 0 , OR
 - The end of study visit will occur after Week 12 when there is loss of muscle tone improvement in the SMG (i.e., a reduction from baseline in MAS score of < 1-point) AND the PGIC score is ≤ 0 . OR
 - Week 36 will be the end of study for all subjects, even those who maintain muscle tone improvement in the SMG (i.e., a reduction from baseline in MAS score of ≥ 1 point) OR PGIC score is ≥ 1 .
- For subjects enrolled after the COVID-19 20 March 2020 screening and randomization hold the end of study will be at Week 12.

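### The visible TEAE tables compare crude percentages over response-dependent follow-up, which can inflate the DAXI arms; add a Day 1 to Week 12 comparison and subject-time rates (should fix)

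*SAP*

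**What the plan says.** **How events are counted.** SAP 9.3 states: "For TEAE summaries, the number and percentage of subjects will be presented by SOC and PT by treatment". It adds: "Subjects will be counted only once for each SOC and for each PT within each SOC". Each entry is therefore a cumulative proportion. The window opens at dosing ("An AE will be considered treatment emergent if the event begins on or after the study medication dose date"), and no closing date common to all subjects is given. Protocol 6.2.2.1 collects an event that "emerges or worsens following administration of investigational product and until the end of trial participation", so the window closes when each subject's own participation ends.

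**How long subjects are followed.** Protocol 3.5 sets a range of 12 to 36 weeks. For subjects enrolled before the hold, Protocol 3.6 and SAP 3.4 allow the final visit at Week 12 if the MAS reduction in the SMG is under 1 point and PGIC is 0 or below. After that, SAP 3.4 says: "The end of study visit will occur after Week 12 when there is loss of muscle tone improvement in the SMG", again together with PGIC of 0 or below. Everyone else continues to Week 36. Subjects enrolled after the hold finish at Week 12, whatever their arm or response.

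**What is planned around this.** SAP 7.1 summarises duration of participation and reasons for discontinuation, but does not link duration to the AE tables. The safety comparison of each dose with placebo is part of the primary objective (Protocol 2.1, SAP 3.1).

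**Discontinuation table.** SAP 9.3 lists "TEAEs resulting in study medication discontinuation by SOC and PT" and a matching listing. The study gives one injection session, and Protocol 4.6 says: "Discontinuation of study treatment is not applicable".

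**The concern.** A proportion that counts each subject once can only rise with follow-up. Here follow-up is longer for subjects who respond, and the trial is planned on the expectation that more DAXI than placebo subjects respond. The DAXI percentages would then include more late background events (infections, falls, intercurrent illness) simply because those subjects were watched longer.

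At stake is the descriptive dose-versus-placebo safety comparison. An apparent excess on DAXI could be an artefact of follow-up. If effect also lasts longer at higher doses, the artefact could look like a dose-response in harm. SAP 7.1 lets a reader see that follow-up differs, but gives no means of correcting any SOC or PT row.

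**Working it through.** **Step 1. The plan's own figure.** The documents give no AE rate or expected follow-up. The related figure that can be checked is the targeted effect in SAP 3.6: 0.9/1.1 = 0.82 and 1.1/1.1 = 1.00, which agrees with the stated 0.8 to 1.0.

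**Step 2. Would exit differ by arm?** Take the MAS condition alone. With reduction normally distributed, SD 1.1 and mean m, the share meeting it is Φ((c − m)/1.1), with c = 1.0, or c = 0.5 as a continuity correction for whole-point scores. Assume a placebo mean reduction of 0.2 to 0.8, and that the planned Week 6 difference of 0.9 to 1.1 persists to Week 12. Example with placebo mean 0.5, difference 0.9, c = 1.0:
- placebo: Φ((1.0 − 0.5)/1.1) = Φ(0.45) = 68%
- DAXI: Φ((1.0 − 1.4)/1.1) = Φ(−0.36) = 36%

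Over the whole range this gives 39 to 77% of placebo and 10 to 46% of DAXI subjects. The added PGIC condition can only lower both.

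**Step 3. Crude percentage under identical event rates.** Let p be the risk of a first event by Week 12, with the same constant hazard in every arm: λ = −ln(1 − p)/12 per week. Let w(t) be the share of pre-hold subjects leaving at visit t (Weeks 12, 16, ..., 36), and s the pre-hold share of all subjects. Then

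crude % = s × Σ w(t)[1 − exp(−λt)] + (1 − s) × p.

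The second term is the same in every arm, so the excess is proportional to s. The values of p, w and s are assumptions; the documents give none of them.

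**Step 4. One case in full (pattern B, p = 20%, s = 100%).** Placebo: 60% leave at Week 12, then 30% of those remaining at each later visit. DAXI: 20%, then 20%. All still in the study leave at Week 36.
- Cumulative risk at Weeks 12, 16, 20, 24, 28, 32, 36: 20.0, 25.7, 31.1, 36.0, 40.6, 44.8, 48.8%.
- Placebo weights: 0.600, 0.120, 0.084, 0.059, 0.041, 0.029, 0.067, giving 26.1%.
- DAXI weights: 0.200, 0.160, 0.128, 0.102, 0.082, 0.066, 0.262, giving 34.8%.
- False excess: 8.8 points before rounding, ratio 1.34. Mean follow-up: 16.7 vs 23.8 weeks.

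**Step 5. Range.** Excess in percentage points, DAXI minus placebo; the true difference is zero throughout. Each pattern gives the Week 12 exit, then the exit per later visit, placebo vs DAXI.

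| Exit pattern | Pre-hold share | Mean follow-up, weeks | p = 10% | p = 20% | p = 30% |
|---|---|---|---|---|---|
| A: 50%, 25% vs 25%, 25% | 100% | 18.6 vs 21.9 | 2.4 | 4.2 | 5.4 |
| A | 50% | 15.3 vs 16.9 | 1.2 | 2.1 | 2.7 |
| B: 60%, 30% vs 20%, 20% | 100% | 16.7 vs 23.8 | 5.1 | 8.8 | 11.1 |
| B | 50% | 14.4 vs 17.9 | 2.6 | 4.4 | 5.5 |
| C: 80%, 40% vs 20%, 15% | 100% | 13.9 vs 25.3 | 8.2 | 14.0 | 17.6 |
| C | 50% | 13.0 vs 18.6 | 4.1 | 7.0 | 8.8 |
| Equal: 40%, 25% in both | any | equal | 0 | 0 | 0 |

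The excess is roughly 2 to 17 points, with 1.2 and 17.6 at the corners. Pattern C is a stress case: its 80% placebo exit lies just above the 77% ceiling of Step 2. Pattern B gives 2.6 to 11.1. With no pre-hold subjects, or with every first event before Week 12, the excess is zero.

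**Step 6. After the fix.** With p = 20%, a Day 1 to Week 12 table shows 20.0% in each arm. A subject-time rate shows −ln(0.8)/12 = 1.86 first events per 100 subject-weeks at risk in each arm. The artefact is gone in both.

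**The case against.** **Exit follows response, not arm.** A reader might infer that placebo subjects leave at Week 12 as a group. They do not: both conditions must hold, and the Week 12 exit is worded as a possibility. A placebo subject improved on either measure stays. This stands, and it makes the excess an expectation that depends on DAXI working.

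**The 24-week figure.** A reader might take Protocol 3.5 to predict that duration here. The text is "With a median duration of effect of at least 24 weeks experienced by adult subjects with cervical dystonia", joined to glabellar-line studies. It justifies up to 36 weeks of follow-up and states no expected duration in upper limb spasticity. Nothing above uses it.

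**Size against noise.** The AE tables are descriptive, with no test. With an assumed 32 per arm, 8.8 points is about 3 subjects, against a standard error of 10 to 12 points at risks of 20 to 40%. The bias also overstates harm on DAXI rather than hiding it. This stands and limits the severity, but a directional bias remains worth removing when removal is cheap.

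**Other safety tables.** A reader might extend the point to QTcF. SAP 9.8 already shows the QTcF categories by visit, Week 12 included, beside the any-visit row, so a common-time comparison exists.

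**Withdrawals because of AEs.** A reader might infer that these are not tabulated, or that the discontinuation table is bound to be empty. Neither is established. SAP 7.1 summarises discontinuation reasons, and Protocol 4.6 records the AE when consent is withdrawn because of one. Part of the SAP 9.3 table list is blacked out, and the CRF item is not visible. What remains is a label that does not fit a single-injection study.

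**Replacing the full-follow-up tables.** This would demote late events, which the longer follow-up exists to capture. Exposure-adjusted rates also dilute early events. With true early risks of 10% vs 20% and mean follow-up of 16.7 vs 23.8 weeks, the rates are 0.10/16.7 and 0.20/23.8, so a risk ratio of 2.0 becomes a rate ratio of 1.4. This stands, so the new outputs should be additions.

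**Conclusion.** The point holds for the visible SAP text and rates as should-fix. Cumulative percentages are combined with follow-up that depends on response in pre-hold subjects. If DAXI works as planned, the DAXI percentages are inflated in expectation even at identical event rates.

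The size of roughly 2 to 17 points rests on an assumed constant hazard, assumed Week 12 risks of 10 to 30%, assumed exit patterns and a 50 to 100% pre-hold share. It shrinks in proportion to the pre-hold share and vanishes if exit patterns match or if first events are confined to the first 12 weeks. Exposure adjustment may be specified in text that is not visible; if so, only the Week 12 tables and the relabelling remain to be considered.

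**What to change.** Keep the full-follow-up n (%) tables and all listings. In SAP 9.3, before database lock:

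1. Add between-arm TEAE tables (overall, SOC/PT, related, serious, maximum severity) limited to onset from Day 1 to Week 12, and name them the primary between-arm safety comparison. Week 12 is the planned minimum follow-up for all subjects, before and after the hold. State how the cut-off date is set, and show how many subjects per arm reached it, since early withdrawals remain.
2. For full follow-up, show subject-weeks at risk and exposure-adjusted incidence rates per arm beside n (%). State that they are to be read with the Week 12 tables, because such rates dilute early events.
3. Relabel the medication-discontinuation TEAE table and listing as TEAEs leading to withdrawal from the study, unless a blacked-out table already covers this.

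Protocol 5.4 ends participation when MAS is back at baseline levels, whereas Protocol 3.6 and SAP 3.4 use a reduction of less than 1 point. These passages must be reconciled, because they set follow-up length.

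The cost is SAP wording and extra table programming. No new data are needed, and the design does not change.
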